### **Nonstructural Dysfunction**

Nonstructural dysfunction is any abnormality resulting in stenosis or regurgitation at the operated valve that is not intrinsic to the valve itself. Nonstructural dysfunction refers to nonstructural problems that result in dysfunction of a study valve *exclusive of thrombosis or infection* diagnosed by reoperation, autopsy, or clinical investigation.

Examples of nonstructural dysfunction include: entrapment by pannus, tissue, or suture; paravalvular leak, inappropriate sizing or positioning, residual leak or obstruction from valve implantation or repair, and clinically significant hemolytic anemia.

Sudden or progressive dysfunction or deterioration of the study valve may be structural, nonstructural, or both as determined by reoperation, autopsy, or clinical investigation.

### **Reoperation**

Reoperation is any operation that repairs, alters or replaces the study valve. The reasons for reoperation are to be reported and may include reasons other than valve-related morbidity, such as recall, excessive noise, or incidental or prophylactic removal. A transcatheter aortic valve valve-in-valve replacement procedure is considered a reoperation.

Thrombolytic or catheter-aided therapy of valve-related morbidity is not considered reoperation; however, the morbid event that prompted the intervention should be reported.

### **Structural Deterioration**

Structural valve deterioration is any change in function of a study valve resulting in an intrinsic abnormality of the valve that causes stenosis or regurgitation.

Structural valvular deterioration includes study valve dysfunction or deterioration *exclusive of infection or thrombosis* as determined by reoperation, autopsy, or clinical investigation. The term structural deterioration refers to changes intrinsic to the valve, such as wear, stent fracture, calcification, leaflet tear, stent creep, and suture line disruption of components (e.g., leaflets) of an operated valve.

### **Valve Thrombosis**

Valve thrombosis is any thrombus, *in the absence of infection*, attached to or near the study valve that occludes part of the blood flow path or that interferes with function of the valve. Valve thrombosis may be documented by operation, autopsy, or clinical investigation. Valve thrombosis is categorized as follows:

- Obstructive valve thrombosis: The accumulation of thrombus on a replacement valve with (potentially) catastrophic hemodynamic or embolic consequences.
- Non-obstructive valve thrombosis: An incidental finding without (potentially) catastrophic hemodynamic consequences (e.g., thrombus on the outflow aspect of the bioprosthesis, etc.)

## Clinical Investigation Plan

### Appendix D: Case Report Form

---

## Statistical Analysis Plan

### 1.0 SYNOPSIS OF STUDY DESIGN

#### 1.1 Purpose of the Statistical Analysis Plan

This statistical analysis plan (SAP) is intended to provide a detailed and comprehensive description of the planned methodology and analysis to be used for [REDACTED], the Trifecta GT PMCF clinical investigation. [REDACTED]

#### 1.2 Clinical Investigation Objectives

The objective of this study is to evaluate the safety and performance of the Trifecta™ GT valve through 5-year follow-up in a prospective, multi-center, real-world setting. This study is intended to satisfy post-market clinical follow-up requirements of CE Mark in Europe. This study is sponsored by Abbott.

#### 1.3 Clinical Investigation Design

This study is a multi-center, prospective 5-year study of approximately 350 subjects intended to be implanted with a SJM Trifecta GT valve. It will be conducted in approximately 35 sites worldwide. [REDACTED]

To ensure an adequate number of subjects at each site, no individual site may enroll more than 10% of the maximum sample size (n=35 subjects) without prior approval from the sponsor.

#### 1.4 Endpoints

There is one primary endpoint and five descriptive endpoints in this clinical study.

##### 1.4.1 Primary Endpoint

The primary safety endpoint is freedom from surgical valve replacement or transcatheter valve-in-valve implantation at 5 years post implant.

##### 1.4.2 Descriptive Endpoints

This section lists descriptive endpoints that will be summarized using descriptive statistics:

- Freedom from all-cause mortality at 5 years post implant
- Freedom from valve related mortality at 5 years post implant
- Freedom from Structural Valve Deterioration (SVD) at 5 years post implant
- Freedom from surgical valve replacement or transcatheter valve Implantation due to SVD at 5 years post implant
- Valve hemodynamic performance (e.g., left ventricular ejection fraction, mean and peak gradients, aortic insufficiency, and effective orifice area via any available/performed echocardiograms) at pre-discharge, 6 months, 3 years, and 5 years post implant.

## Statistical Analysis Plan

### 2.0 ANALYSIS CONSIDERATIONS

#### 2.1 Analysis Population

#### 2.2 Statistical Methods

##### 2.2.1 Descriptive Statistics for Continuous Variables

Continuous variables will be summarized with the numbers of observations, mean, standard deviation and range.

##### 2.2.2 Descriptive Statistics for Categorical Variables

Categorical variables will be summarized with subject counts and percentages/rates.

##### 2.2.3 Survival Analyses

Survival analysis will be conducted to analyze all time-to-event variables. Subjects without events will be censored at their last known event-free time point. Survival curves will be constructed using Kaplan-Meier estimates.

##### 2.2.4 Annualized Rates

The annualized event rate will be estimated using the number of late events (those occurring > 30 days post implant) divided by the total patient time in years, expressed as a percentage.

For each subject, Patient time will be the time from implant to last contact date (date of death, explant, withdrawal, or last known visit).

Total patient time will be calculated as the sum of late post-operative follow up time in years.

#### 2.3 Endpoint Analysis

There will be no hypothesis testing in this clinical investigation. Results will be analyzed and presented descriptively.

##### 2.3.1 Primary Endpoint

The primary endpoint, freedom from surgical valve replacement or transcatheter valve-in-valve implantation at 5 years post implant, will be summarized using Kaplan-Meier methods and annualized rate as described in Section 2.2.3 and 2.2.4.

##### 2.3.2 Descriptive Endpoints

The following describes the additional endpoints that will be analyzed descriptively at 5-years post procedure:

- Freedom from all-cause mortality at 5 years post implant
- Freedom from valve related mortality at 5 years post implant

## Statistical Analysis Plan

- Freedom from Structural Valve Deterioration (SVD) at 5 years post implant
- Freedom from surgical valve replacement or transcatheter valve Implantation due to SVD at 5 years post implant
- Valve hemodynamic performance (e.g., left ventricular ejection fraction, mean and peak gradients, aortic insufficiency and effective orifice area via any available/performed echocardiograms) at pre-discharge, 6 months, 3 years and 5 years post implant.

All time-to-event endpoints will be summarized using survival estimates as described in Section 2.2.3.

Valve hemodynamic performance endpoint variables will be analyzed by valve size for each specified follow up visit using appropriate summary statistics as discussed in sections 2.2.1 and 2.2.2.

### 2.4 Sample Size Calculations

[REDACTED]

### 2.5 Interim Analysis

No formal interim analyses are planned for this trial. As such, no formal statistical rule for early termination of the trial is defined. Interim study reports with descriptive analysis may be produced for regulatory or reimbursement purposes.

### 2.6 Timing of Analysis

Study endpoints will be analyzed after the completion of the 5-years post procedure follow up.

### 2.7 Study/Trial Success

The study has one primary endpoint without formal hypothesis. The primary endpoint result will be compared with data reported in the literature.

### 2.8 Subgroups Analysis

No subgroup analyses is planned.

### 2.9 Handling of Missing Data

All analysis will be based on available data. No missing data imputation is planned for this trial.

### 2.10 Multiplicity Issues

No hypothesis testing will be performed; therefore, there will be no adjustments to multiplicity.

[REDACTED]

[REDACTED]

## Statistical Analysis Plan

### 2.11 Adjustments for Covariates

Unless otherwise specified, no adjustments for covariates will be made for any of the variables in the analyses.

### 3.0 DESCRIPTIVE ENDPOINTS AND ADDITIONAL DATA

#### 3.1 Baseline and Demographic Characteristics

Baseline and medical characteristics such as age, gender, Euroscore, STS mortality risk score, cardiovascular history, etc. will be summarized using appropriate summary statistics.

#### 3.2 Adverse Events

All adverse events (AEs) reported will be summarized by seriousness (serious AE vs. nonserious AE), primary relationship (device, procedure, and unrelated).

The following definitions will apply:

- AE: Adverse Events (Non-serious and non-device or procedure related)
- ADE: Adverse Device Effects (Non-serious and device or procedure related)
- SAE: Serious Adverse Events (Serious and non-device or procedure related)
- SADE: Serious Adverse Device Effects (Serious and device or procedure related)

Summaries will be presented in terms the number of events and number and percentage of subjects with events. Categories will be non-overlapping.

All events adjudicated as related or possibly related to COVID-19 will also be summarized.

All CEC adjudicated adverse events will also be summarized in terms of the number of events, number and percentage of subjects with events.

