### 8.2 Safety Reporting

Safety surveillance and the safety reporting by the investigator starts as soon as the subject is enrolled in this clinical study. Refer to Section 5.3 for the definition of subject enrollment.

The safety surveillance and the safety reporting will continue until the last study visit has been performed, the subject is deceased, the subject/investigator concludes his participation into the clinical study or the subject withdrawal from the clinical study.

The PI will report the event to the IRB/EC per their reporting requirements. The following are reportable events per this CIP (see Appendix B for definitions):

- Adverse Device Effects (regardless of seriousness)
- Serious Adverse Events (regardless of severity) including those specified in Edmunds Criteria which include:
  - Structural valve deterioration

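### SAP 3.2 gives the names AE, ADE, SAE and SADE to four non-overlapping cells, so counts shown under those names will not match the protocol's Appendix B definitions

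*SAP*

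**What the plan says.** SAP Section 3.2 opens with a general plan: all reported adverse events "will be summarized by seriousness (serious AE vs. nonserious AE), primary relationship (device, procedure, and unrelated". It then sets out definitions that are to govern the tables, one for each cell:

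- The serious and related cell is given as "SADE: Serious Adverse Device Effects (Serious and device or procedure related".
- The serious and unrelated cell is given as "SAE: Serious Adverse Events (Serious and non-device or procedure related".
- The non-serious and related cell is given as "ADE: Adverse Device Effects (Non-serious and device or procedure related".
- The non-serious and unrelated cell is given as "AE: Adverse Events (Non-serious and non-device or procedure related".

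Two further rules follow: "Summaries will be presented in terms the number of events and number and percentage of subjects with events", and "Categories will be non-overlapping". The section also plans a separate summary, by events and by subjects, of the events adjudicated by the Clinical Events Committee (CEC).

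The protocol uses the four names differently. Section 8.2 introduces its reporting list with "The following are reportable events per this CIP (see Appendix B for definitions". It asks for device effects whether serious or not, and for serious adverse events, among which it places structural valve deterioration, nonstructural dysfunction, valve thrombosis and death. In Appendix B:

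- an AE is any untoward occurrence, device-related or not, and procedure-related events are included;
- an SAE is an AE with one of the listed serious outcomes, with no condition on cause;
- an ADE is an AE related to use of the device, with no condition on seriousness;
- a SADE is an ADE with a serious consequence.

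**The concern.** Events are reported under one set of definitions and tabulated under another, with the same four names on both. A reader who takes the SAE row in its protocol sense will understate serious events, because that row leaves out the ones judged related to the valve or the operation. A reader who takes the SADE row in its protocol sense may attribute purely procedural events to the device. Safety is part of the stated objective, and the study is meant to meet a CE Mark follow-up requirement, so these rows are likely to be read closely.

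SAP 3.2 is also inconsistent within itself. Its first sentence speaks of serious AEs and of all AEs, while its own definition makes an AE non-serious and unrelated.

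**Working it through.** The plan states no figure to reproduce, and the documents give no event counts. The check is a comparison of sets.

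**Reading the wording.** The phrase for the unrelated cells could be parsed as (not device-related) or (procedure-related). Serious procedure-related events would then fall in both the SAE and the SADE rows, which the non-overlap rule forbids. The mirrored ADE and SADE definitions leave one reading: related to neither device nor procedure.

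**Cells.** Split all reported events six ways. Let s or n mark serious or non-serious. Let D mean device-related in the Appendix B sense, P procedure-related but outside the Appendix B device-effect definition, and U related to neither. Device-related in the SAP is assumed to mean the same as D.

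| Label | Appendix B count | SAP 3.2 count | SAP minus Appendix B |
|---|---|---|---|
| AE | sD+sP+sU+nD+nP+nU | nU | −(sD+sP+sU+nD+nP) |
| SAE | sD+sP+sU | sU | −(sD+sP) |
| ADE | sD+nD | nD+nP | nP − sD |
| SADE | sD | sD+sP | +sP |

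The four SAP rows sum to nU + sU + (nD+nP) + (sD+sP), which is the Appendix B AE total. Nothing is dropped; events are filed under different names.

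**Direction.** The SAE row can only be too low by the protocol's definition, and the SADE row only equal or too high. The ADE row loses sD and gains nP, so its net direction is unknown.

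**Size of the SADE difference.** Appendix B already counts as device effects those events that arise from inadequate instructions for implantation, from use error or from malfunction. Some procedure-related events will therefore be D and not P. If all of them are, sP = 0 and the SADE row agrees with the protocol.

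**Subjects.** Adding the SAE and SADE rows restores the serious event total: sU + (sD+sP). It does not restore the number of subjects. With A subjects in one row and B in the other, out of N, the number with any serious event lies between max(A, B) and min(N, A+B). The planned summary by seriousness supplies that number directly.

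**Device-only serious events.** Suppose seriousness and relationship are tabulated separately, alongside the four cells. For sD, sP, nD and nP the report then gives four sums: sD+sP, nD+nP, sD+nD and sP+nP. The first two and the last two have the same total, so only three are independent, and four unknowns cannot be solved from them. The value of sD is only bounded: at least max(0, (sD+nD) − (nD+nP)) and at most min(sD+nD, sD+sP). If the two axes are crossed, sD is shown. The SAP does not say which is intended.

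**The case against.** The best defence is that this is a table convention with its definitions printed beside it. It has real force:

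- The related serious events are shown, under SADE.
- Seriousness and relationship are each planned as summaries, and these give events and subjects. A reader might infer that serious related events are missing from the safety report, or that the number of subjects with any serious event is unavailable. The documents support neither.
- The CEC summary, and the Kaplan-Meier analyses of mortality, structural deterioration and reintervention in SAP 2.3, do not use the four labels.
- SAP 3.2 lists seriousness and relationship in one sentence, so crossing them is a natural reading. The device-only serious count needs an explicit statement; it is not shown to be absent.

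Three other inferences are tempting and also fail:

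- **The AE row would be almost empty, or the ADE row could not exceed the protocol's ADE count.** Protocol 8.2 lists only ADEs and SAEs as reportable. But Sections 5.4.3 and 5.4.4 and Table 2 collect adverse events at visits without that limit. Sections 5.4.2 and 5.8 require a 30-day collection period after a failed implant. Section 8.2.2 requires an adverse event form for any complaint that involves one. Non-serious unrelated and non-serious procedure-related events can therefore enter.
- **Relationship to procedure is not collected.** Section 8.2 names only relationship to device among the items to record, but it allows further information, and the case report form is not in the text available. The SAP presupposes that the item exists.
- **The discrepancy is large.** Any percentage would rest wholly on assumed event counts.

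What the defence does not answer is the naming. A non-overlapping table is legitimate, but the protocol had already defined these four names as different sets, and the SAP says its own definitions govern.

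**Conclusion.** The contradiction is certain and its effect is bounded. Followed as written, SAP 3.2 yields event counts and subject percentages under protocol-defined names that do not follow the protocol's definitions. The SAE row is short by every serious device- or procedure-related event, the ADE row lacks serious device effects, the AE row is reduced to one of the six cells, and the SADE row may include procedural events that are not device effects. No data are lost, no endpoint estimate changes, and the serious total remains available elsewhere in the same section. The size cannot be determined from the documents. The conclusion rests on reading the unrelated cells as related to neither device nor procedure, which the non-overlap rule forces. The SADE comparison also assumes that device-related has the same meaning in both documents.

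**What to change.** In SAP 3.2:

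1. Replace the four definitions with a reference to protocol Appendix B, and report AE, SAE, ADE and SADE on that basis, each by number of events and by number and percentage of subjects. State that these rows overlap by design.
2. Keep the non-overlapping table, but as seriousness crossed with device, procedure and unrelated, under neutral labels such as serious, related and serious, unrelated. The device-only serious count is then visible.

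When the table shells are revised, confirm that the case report form records relationship to procedure.

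The cost is SAP wording, table shells and a few extra rows. Site reporting and the endpoint analyses are unchanged, and no new data are needed provided relationship to procedure is already recorded, as the SAP presupposes.

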#### 5.10.2 Clinical Events Committee (CEC)

An independent CEC will be established for the study to provide review and adjudication of pre-defined clinical events (e.g. Edmunds Criteria events). The primary function, responsibilities and membership of the CEC will be described in detail in a CEC charter.

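### Five valve-safety event categories are planned, in the visible text, only as counts and crude 5-year percentages, with no allowance for drop-out and no early/late split

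*SAP*

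**What the plan says.** Protocol 5.10.2 sets up a CEC to "provide review and adjudication of pre-defined clinical events", with Edmunds events as the example. Protocol 8.2 lists the Edmunds categories that sites must report: SVD, nonstructural dysfunction, valve-related embolism, valve thrombosis, major bleeding, endocarditis and death.

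For the analysis of adjudicated events, SAP 3.2 states: "All CEC adjudicated adverse events will also be summarized in terms of the number of events, number and percentage of subjects with events". It gives no person-time measure, no time-to-event estimate and no division by time since implant.

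SAP 2.2.4 does define a person-time measure, the "number of late events (those occurring > 30 days post implant) divided by the total patient time in years". Its only visible use is in SAP 2.3.1, where the primary endpoint "will be summarized using Kaplan-Meier methods and annualized rate as described in Section 2.2.3 and 2.2.4". SAP 2.3.2 and Protocol 6.1.2 give Kaplan-Meier estimates for all-cause death, valve-related death, SVD and reintervention due to SVD.

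**The concern.** The study objective is safety and performance over 5 years. After reintervention, SVD and death, the five remaining Edmunds categories are the main evidence on valve safety.

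Two features of the planned summary weaken that evidence:

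- **Drop-out.** Safety reporting stops at withdrawal (Protocol 8.2), and loss to follow-up is a listed reason for withdrawal (Protocol 5.8). In a crude percentage, a subject lost in year 2 counts as event-free to year 5. The less complete the follow-up, the lower the percentage, so the error favours the device.
- **Timing.** One percentage combines events in the first 30 days with events years later. Reporting begins once implantation has been attempted (Protocol 5.3 and 8.2). The major bleeding definition in Protocol Appendix B counts bleeding that needs transfusion and excludes no perioperative period. Operative bleeding could therefore dominate the figure and obscure the late rate.

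**Working it through.** There is no stated figure to reproduce. The plan gives no event, death or drop-out rate for these categories, and the basis of the sample size is redacted. The check sets the sections side by side and then illustrates the size.

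**1. Which events lack a time-based estimate?**

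| Event | Time-based estimate in the visible text |
|---|---|
| Valve replacement or valve-in-valve | Kaplan-Meier and annualized rate (SAP 2.3.1; Protocol 6.1.1.1) |
| All-cause death, valve-related death, SVD, reintervention due to SVD | Kaplan-Meier (SAP 2.3.2; Protocol 6.1.2) |
| Nonstructural dysfunction, embolism, valve thrombosis, major bleeding, endocarditis | None |

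**2. Size of the understatement.** From the documents: T = 5 years and N = 350. The following are assumptions:

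- constant hazards;
- event hazard h = 1% per year;
- 5-year death probability 10%, so m = −ln(0.90)/5 = 0.02107;
- 5-year drop-out probability (withdrawal or loss) of 0 to 30%, with w = −ln(1 − p)/5;
- all implanted subjects as the denominator of the percentage.

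Cumulative incidence with death as a competing event and no drop-out is h/(h+m) × (1 − exp(−(h+m)T)) = 0.01/0.03107 × (1 − exp(−0.1554)) = 4.63%.

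The crude percentage is h/(h+m+w) × (1 − exp(−(h+m+w)T)):

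| Drop-out over 5 years | w per year | Crude % | Relative shortfall | Shortfall, points |
|---|---|---|---|---|
| 0% | 0 | 4.63 | 0 | 0 |
| 10% | 0.02107 | 4.40 | 5.0% | 0.23 |
| 20% | 0.04463 | 4.16 | 10.1% | 0.47 |
| 30% | 0.07133 | 3.91 | 15.5% | 0.72 |

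Varying h over 0.5% to 2% per year and deaths over 0 to 20% hardly changes the relative shortfall. It stays at 4.8–5.1%, 9.8–10.3% and 15.1–15.8% for 10%, 20% and 30% drop-out.

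**3. Does death cause the understatement?** No. In the 0% drop-out row the crude percentage equals the cumulative incidence despite 10% deaths. One minus Kaplan-Meier with deaths censored would be 1 − exp(−0.05) = 4.88%, above the cumulative incidence. Explant works like death: afterwards the study valve can no longer cause an event.

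**4. Does the rate in SAP 2.2.4 solve it?** Yes, once its denominator is settled. The section gives two definitions: "Patient time will be the time from implant to last contact date", and "Total patient time will be calculated as the sum of late post-operative follow up time in years". The first includes days 0–30, the second does not, while the numerator counts late events only.

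Take 10% deaths and 20% drop-out, with s = m + w = 0.06570 and patient time ending at death or drop-out:

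- Time from implant: 350 × (1 − exp(−5s))/s = 350 × (1 − 0.72)/0.06570 = 1492 patient-years.
- Late time: 350 × (exp(−s × 30/365.25) − 0.72)/s = 1463 patient-years.
- Expected late events: 0.01 × 1463 = 14.63.
- Rate over late time: 14.63/1463 = 1.00% per year. Rate over time from implant: 14.63/1492 = 0.98% per year.

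Late events over late time return 1.00% per year at every drop-out level tried. The mixed form is about 2% too low.

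**The case against.** The strongest reply is that this is reporting advice on secondary safety tables. There is no hypothesis test (SAP 2.3), and the planned literature comparison concerns the primary endpoint (SAP 2.7), which already has Kaplan-Meier and an annualized rate. SAP 3.3 summarizes early terminations by reason, so readers will see the attrition. The gap of 0.2 to 0.7 points is small beside sampling error: for 4.5% of 350 subjects, the 95% half-width is 1.96 × √(0.045 × 0.955/350) = 2.2 points. All of this stands and sets the severity. It does not remove the point, because the error is systematic and in the device's favour.

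A second reply is that SAP 2.2.3 promises survival analysis for every time-to-event variable. No section names these five categories as such variables, so an analyst has no instruction to go further. Redacted text or the CEC charter may say more. SAP 3.2 also gives no denominator for the percentage, so the use of all implanted subjects is an assumption here.

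A third reply concerns timing. SAP 3.2 also summarizes reported adverse events by relationship to device or procedure, and the embolism definition already leaves out the immediate perioperative period. A reader might infer that procedural and valve-related events cannot be told apart at all; that goes too far. But the relationship summary is not stated to be by event category, and the definitions in the same section combine device and procedure relationship in one class. Major bleeding therefore remains the clearest case for an early/late split.

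**Conclusion.** The point holds for five categories: nonstructural dysfunction, valve-related embolism, valve thrombosis, major bleeding and endocarditis. For these, the visible plan offers only counts and crude percentages over 5 years. Such percentages understate incidence under withdrawal and loss to follow-up, by about 5% to 16% in relative terms for 10% to 30% drop-out. The size rests on assumed rates and constant hazards; the direction does not depend on the particular rates.

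Two stronger readings are not supported. A reader might infer that every adjudicated valve event lacks a time-based estimate, but SVD, mortality and reintervention have Kaplan-Meier estimates. A reader might also count deaths and explants among the sources of understatement, but they are competing events and produce none.

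Severity is minor. The primary result and its literature comparison are unaffected.

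**What to change.** First, amend SAP 2.2.4 so that patient time has one definition and late events are divided by late time, meaning time after day 30.

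Then add to SAP 3.2, for each of the five categories and alongside the planned counts and percentages:

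- early events (up to 30 days) as a percentage of implanted subjects, since the annualized rate leaves them out;
- late events (after 30 days) per 100 late patient-years, with an exact Poisson 95% confidence interval.

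A 5-year cumulative incidence with death and explant as competing events would be an acceptable alternative to the late rate. The denominator of the existing percentages should be stated too.

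The cost is one extra table. Event dates are collected under Protocol 8.2, and last-contact dates are already needed for SAP 2.2.4. The limitation is that a late rate is not a 5-year risk and is easiest to interpret when the hazard is roughly constant.

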### 6.3 Timing of Analysis

The analyses for final report will be conducted on datasets locked after all enrolled subjects have had the 5-year study visit (excepting deaths, withdrawals and loss-to-follow-up before 5 years) or crossed the 5-year visit window without a visit (missed visit).

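### SAP 3.2 gives CEC-adjudicated non-endpoint events no time-based summary; with an all-subjects denominator, the percentage sits slightly at or below the 5-year incidence when subjects are lost

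*SAP*

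**What the plan says.** Protocol 5.10.2 states: "An independent CEC will be established for the study to provide review and adjudication of pre-defined clinical events". It offers the Edmunds criteria as an example and leaves the list to a charter that is not public. Protocol 8.2 names the Edmunds events as reportable. Of these, endocarditis, embolism, valve thrombosis, nonstructural dysfunction and major bleeding appear nowhere among the endpoints in SAP 1.4.

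The summary for adjudicated events is in SAP 3.2: "All CEC adjudicated adverse events will also be summarized in terms of the number of events, number and percentage of subjects with events". No denominator is given there, and the analysis-population text (SAP 2.1, protocol 6.1.1.2) is not visible.

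Time-based methods are assigned elsewhere:
- SAP 2.2.3, general methods: "Survival analysis will be conducted to analyze all time-to-event variables".
- SAP 2.3.1, the primary endpoint: it "will be summarized using Kaplan-Meier methods and annualized rate as described in Section 2.2.3 and 2.2.4".
- SAP 2.3.2: "All time-to-event endpoints will be summarized using survival estimates as described in Section 2.2.3".

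Three provisions determine what happens to a subject who leaves early. Under protocol 8.2, safety reporting can end when "the subject/investigator concludes his participation into the clinical study or the subject withdrawal from the clinical study". Protocol 6.3 locks the final data after the 5-year visits, "excepting deaths, withdrawals and loss-to-follow-up before 5 years". SAP 2.9 adds: "All analysis will be based on available data. No missing data imputation is planned for this trial". SAP 3.3 tabulates the reasons for early termination.

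**The concern.** The objective is safety through 5 years, yet for these valve complications the only planned percentage is neither a 5-year risk nor a rate per patient-year. A subject who withdraws event-free in year 2 contributes nothing to the numerator afterwards. If the denominator is everyone enrolled or implanted, that subject remains in it as though followed for 5 years. The termination table shows the incompleteness but does not correct for it.

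At stake is how the complication table reads beside other reports of valve complications, and how a descriptive interim report under SAP 2.5 reads when subjects have unequal follow-up. No hypothesis test and no primary result depends on it.

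**Working it through.** **Inputs.** From the documents: about 350 subjects and 5 years of follow-up. They state no event, death, explant or loss rate, so there is no plan figure to reproduce and the following are assumptions. Hazards are constant: event h = 0.01 per year, death d = 0.03, explant x = 0.005. Withdrawal or loss l is 0, 0.01, 0.02 or 0.05.

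**Target.** The 5-year cumulative incidence of first event with the valve in place, death and explant competing:

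h/(h+d+x) × [1 − exp(−5(h+d+x))] = (0.01/0.045) × [1 − exp(−0.225)] = 0.2222 × 0.2015 = 4.48%.

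**Crude percentage, all subjects in the denominator.** Events are seen only before loss:

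h/(h+d+x+l) × [1 − exp(−5(h+d+x+l))].

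For l = 0.02: (0.01/0.065) × [1 − exp(−0.325)] = 0.1538 × 0.2775 = 4.27%.

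The share leaving without the event is the same expression with l in place of h as the leading numerator. The last column divides the crude value by one minus that share, which is the result if lost subjects were dropped from the denominator.

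| Loss per year | Leave without event | Crude % | Gap (points) | Relative | Subjects of 350 | Lost subjects dropped |
|---|---|---|---|---|---|---|
| 0 | 0 | 4.48 | 0 | 0 | 0 | 4.48 |
| 1% | 4.4% | 4.37 | 0.11 | 2.4% | 0.4 | 4.57 |
| 2% | 8.5% | 4.27 | 0.21 | 4.7% | 0.7 | 4.67 |
| 5% | 19.9% | 3.98 | 0.50 | 11% | 1.7 | 4.97 |

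The zero-loss row shows that death and explant cause no bias against this target; only withdrawal and loss do.

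**Sensitivity.** For event hazards of 0.003 and 0.02, the relative gap at 1%, 2% and 5% loss is 2.4/4.7/11.2% and 2.3/4.6/11.0%. With half the 5-year event hazard in year 1 (0.025, then 0.00625), it falls to 1.6/3.2/7.7%. Events that cluster late give a larger gap.

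**Informative loss.** Let the event hazard after leaving be k times that before. At 5% loss the truth is 3.98% (k = 0), 4.23% (k = 0.5), 4.48% (k = 1) or 4.96% (k = 2). The crude 3.98% is exact only at k = 0. A cumulative incidence that censors at loss targets 4.48%. It is closer to the truth once k exceeds about 0.5, and too high for k below 1.

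**Against sampling error.** The 95% half-width for one category is 1.96 × √(0.0448 × 0.9552/350) = 2.17 points, above every gap in the table. In simulation (n = 350, 4,000 runs) the standard deviations for crude and Aalen-Johansen are 1.08 and 1.13 points at 2% loss, and 1.05 and 1.18 at 5%. The crude root mean squared error is then √(1.08² + 0.21²) = 1.10 against 1.13, and √(1.05² + 0.50²) = 1.16 against 1.18.

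**Interim report.** With follow-up assumed spread evenly over 1 to 3 years and 2% loss, the crude percentage is 1.87%; with no loss it is 1.91%. The cumulative incidence is 1.91% at 2 years and 2.81% at 3 years.

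**The case against.** The best defence is that a table of observed events is correct as such. SAP 3.2 never calls the percentage a 5-year risk, nothing is tested, and the time-to-event endpoints already use Kaplan-Meier. Events that cause valve-related death, or lead to valve replacement or valve-in-valve, enter those endpoints. All of this stands, and it limits the priority.

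SAP 2.2.3 is worded more widely than endpoints, so it permits survival estimates for these events. It does not commit to them: 3.2 does not refer to it and specifies a different summary. Redactions and the unseen charter mean that the affected categories are expected, not certain.

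The mean squared error comparison also stands. At this size, the variance added by the cumulative incidence outweighs the bias removed. The gain is a quantity with a defined meaning at 5 years, not a more accurate number.

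A reader might infer that the percentage must be too low whatever the reason for loss. The documents do not support that. With no later events among lost subjects it is exact, and if they were dropped from the unstated denominator it would be too high (4.57% to 4.97% against 4.48%).

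A reader might also set the interim 1.87% against the 3-year 2.81% and blame loss for the difference. Loss explains only 0.04 points. The crude figure matches a 2-year incidence; the real difficulty is that no time point is attached to it.

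**Conclusion.** The point holds as a low-priority, inexpensive improvement. SAP 3.2 commits to no time-based summary for CEC-adjudicated events that are not endpoints. With all enrolled or implanted subjects in the denominator, the crude percentage is at or below the 5-year cumulative incidence once subjects withdraw or are lost. On the assumed rates the shortfall is 0.1 to 0.5 points, 2% to 11% relative, for yearly loss of 1% to 5%.

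This rests on the denominator, on event and loss rates that the documents do not give, on roughly constant hazards, and on non-informative loss. The primary, mortality and SVD endpoints are unaffected, so a conclusion that the study's main safety results are biased would not follow.

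**What to change.** In SAP 3.2, keep the counts, state the denominator, and add for each CEC-adjudicated category that is not an endpoint:

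1. The annualized late-event rate of SAP 2.2.4 with a 95% confidence interval.
2. The 5-year cumulative incidence of first event from implant (Aalen-Johansen) with a 95% confidence interval, with death competing and censoring at withdrawal, loss or last contact.

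State that the cumulative incidence covers events while the study valve is in place, and on that definition treat explant as competing. The statement is needed because Appendix B ties only valve thrombosis and nonstructural dysfunction to the study valve; major bleeding, embolism and endocarditis are defined more widely. Say how valve-in-valve is handled, since the study valve then remains in the patient. Do not take the SAP 2.2.4 last contact date as the censoring date for explanted subjects, because it includes explant. Censoring explants would give (0.01/0.04) × [1 − exp(−0.20)] = 4.53% instead of 4.48%.

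In any SAP 2.5 interim report, give the same summaries at a stated time point.

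The cost is a wording change and a few more table rows, with no new data. Intervals widen slightly, the cumulative incidence assumes non-informative loss, and a single annualized rate reads best when the late hazard is roughly constant.
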